## **STUDY PROTOCOL**

### **STUDY RATIONALE**

Caring for individuals living with dementia presents unique challenges for caregivers, including changing roles and responsibilities, financial concerns and planning, increased emotional and health strains, and decreased well-being. Research has found significant benefits from caregivers who participate in evidence-based programs. However, many of these programs are not scalable nor sustainable outside of a research context. To date, few studies have leveraged technology to address this issue for engaging and intervening with informal family and friend caregivers.

### **DESCRIPTION OF THE *KINTO CARE COACHING INTERVENTION* PROGRAM**

*Kinto Care Coaching Intervention* is an innovative program that uses technology via a mobile app to address the needs of informal caregivers of persons living with dementia. Program components include: 1) an initial assessment of care needs; 2) an initial one-on-one virtual care coaching meeting that develops an Action Plan that includes both financial and caregiver support goals; 3) interactive and on-going support and educational resources through the mobile app; 4) access to support groups; and 5) on-going chat groups, with both their care coach and support group peers.

### **CONCEPTUAL MODEL AND STUDY HYPOTHESES**

The Stress Process Model (SPM) for Caregivers was the conceptual model used for the study premise and for selecting measures and study hypotheses. The SPM has been widely used in research on stress and coping for caregivers. The domains of the SPM include: 1) Background and Care Context, 2) Objective and Subjective Stressors, 3) Coping and Social Support Resources, 4) Secondary Stressors: Role and Intra-Psychic Strain, and 5) Psychosocial Well-Being Outcomes. Prior studies extend the SPM's category of "coping and social support" to include interventions. For the current study, the *Kinto Care Coaching Intervention* was conceptualized as such in improving outcomes for caregivers. The SPM guided study hypotheses that included hypothesized significant improvements for participants in the intervention condition as compared to participants in the waitlist control condition for the following secondary stressors and psychosocial well-being outcomes : Unmet Needs; Unmet Needs Distress; Financial Self-Efficacy; Dyadic Relationship Strain and Role Captivity; Emotional Health Strain; Caregiver Mastery; Personal Gain; Loneliness; Caregiver Burden; Anxiety Symptoms; and Depressive Symptoms. Exploratory hypotheses also were examined and included measures of Instrumental Activities of Daily Living (IADL)/Personal Activities of Daily Living (PADL) Difficulty; IADL/PADL Distress; Cognitive Difficulty; Cognitive Distress; Behavioral Frequency; and Behavioral Distress.

### **DESIGN AND PROCEDURES**

A randomized controlled trial research design was used to examine the efficacy of the *Kinto Care Coaching Intervention*. After consenting to participate in the study, caregivers completed the baseline/Time 1 survey and were then randomly assigned to the intervention condition or the waitlist control condition. Participants in the intervention condition received the *Kinto Care Coaching Intervention* that used technology via a mobile app to implement the 6-week structured protocol that consisted of the following: 1) initial assessment of care needs; 2) an initial one-on-one virtual care coaching meeting that developed an Action Plan that included both financial and caregiver support goals; 3) interactive and on-going support and educational resources through the mobile app; 4) access

to support groups; and 5) on-going chat groups, with both their care coach and support group peers. Participants randomly assigned to the waitlist control condition were eligible to receive a modified version of the intervention after completion of the study.

To examine intervention efficacy, outcomes were assessed across time that included both short-term and long-term impacts. In total, participants completed 3 surveys: Time 1 (Baseline); Time 2 (after program completion); and Time 3 (45 days after Time 2). All evaluation surveys were completed via Survey Monkey. Once participants completed all 3 of the evaluation surveys, they received a \$120.00 gift certificate as compensation for their time.

## **II. Statistical Analyses Plan**

### **Preliminary Data Analyses:**

Data were cleaned including examining missing data and addressing any out-of-range values. All Time 1 measures were tested for reliability using Cronbach's alpha, with alphas equal to or greater than .70 demonstrating good reliability. Independent t-tests, one-way ANOVAs, and chi square tests were conducted to ensure random assignment resulted in equivalent groups between the intervention and waitlist control conditions on select demographic and caregiving characteristics and to identify covariates to include in subsequent analyses. With respect to attrition analyses, independent t-tests, one-way ANOVAs, and chi-square tests were used to examine if there were any significant differences on select demographic and caregiving characteristics and the Time 1 scale scores for each outcome between participants who completed the study protocol and those who did not.

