### **Primary Analyses:**

To examine intervention efficacy, outcomes were assessed across time that included both short-term and long-term impacts. Separate 2 (condition: intervention, waitlist control) x 3 (time: Time 1, Time 2, Time 3) repeated measures general linear models were used to examine mean group differences across time between the intervention and waitlist control groups for each outcome measure. The repeated measures analyses indicated whether there was any significant change across time for each outcome measure based on whether participants received the intervention or had not received the intervention. Employment status was included as a covariate in all analyses to control for the significant difference found at baseline between the two conditions. For significant outcomes that did not meet the Sphericity assumption, the Greenhouse-Geisser correction was used and reported for degrees of freedom. For outcome measures that were found to be significant, additional post-hoc pairwise comparison with a Bonferroni correction were conducted to examine where the change occurred across the different data collection periods (i.e., Time 2, Time 3).

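### The attrition check uses only Time 1 outcome scores and pools all non-completers, so a null result does not show that loss between Time 2 and Time 3 is harmless

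*Combined protocol and SAP*

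**What the plan says.** The SAP describes one attrition check, under Preliminary Data Analyses. The method is univariate: "independent t-tests, one-way ANOVAs, and chi-square tests were used to examine if there were any significant differences". The variables are background characteristics and "the Time 1 scale scores for each outcome between participants who completed the study protocol and those who did not". For outcomes, Time 1 is explicit. For the characteristics no time point is given; the same description is used for the check of random assignment, so I read them as baseline. Non-completers form one group, and no comparison by arm is described.

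Design and Procedures gives the schedule: "Time 1 (Baseline); Time 2 (after program completion); and Time 3 (45 days after Time 2" (that is, three surveys, the last 45 days after the second). A caregiver who answers Time 2 and is then lost has therefore left Time 2 scores on every outcome.

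Primary Analyses uses all three time points, in separate "2 (condition: intervention, waitlist control) x 3 (time: Time 1, Time 2, Time 3) repeated measures general linear models". It does not say what happens to a caregiver with a missing survey. The only other provision is general: "Data were cleaned including examining missing data and addressing any out-of-range values".

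**The concern.** For a caregiver lost after Time 2, the Time 2 score is the only outcome measured after randomisation, and so the only record of how she responded to the programme. The check leaves it out. If caregivers leave because they did worse than their starting point predicted, their Time 1 scores need not differ from anyone else's, and the check returns a null result at its chance rate.

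At stake is what a null result is allowed to mean. No missing-data method or sensitivity analysis is described, so this comparison is the only stated safeguard for the longer-term result. If it is taken as reassurance, the caregivers analysed at Time 3 could still be selected on their response after randomisation, and differently in the two arms.

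**Working it through.** **Inputs.** The documents give no sample size, alpha, drop-out rate, SD or correlation, so there is no planned figure to reproduce. From the plan I take the survey order, the variables in the attrition check and the 2 x 3 model. Everything else is assumed:

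- 50 to 100 caregivers per arm, and a true effect of 0.4 SD at both follow-ups
- correlation r = 0.6 between any two surveys
- 20% drop-out, all of it after Time 2
- in the intervention arm, drop-out log-odds rise by 1 per SD of a worse value of the driver; in the waitlist arm drop-out is random
- two-sided 5% tests, with scores oriented so that higher is better.

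**Step 1: what Time 1 can show.** Within an arm, write Time 2 = r x Time 1 + sqrt(1 - r^2) x e, with e independent of Time 1.

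- If drop-out depends on e, leavers and stayers have the same Time 1 distribution, and the test rejects at 5%.
- If drop-out depends on the Time 2 level, leavers differ at Time 1 by r times their Time 2 difference, so part of the signal is visible.

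**Step 2: detection and complete-case bias by simulation** (ranges run from 50 to 100 per arm).

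| Driver of drop-out | Time 1 test, arms pooled | Time 1 test, intervention arm | Time 2 adjusted for Time 1, intervention arm | Bias at Time 2 | Bias at Time 3 |
|---|---|---|---|---|---|
| Time 2 not predicted by Time 1 | 5% | 5% | about 70-95% | +0.14 SD | +0.05 SD |
| Change from Time 1 to Time 2 | 13-20% | about 20-35% | about 60-89% | +0.15 to +0.16 SD | +0.08 SD |
| Time 2 level | 18-32% | about 30-54% | not tabulated; see step 5 | +0.07 SD | about 0 |

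**Step 3: the biases by hand.** Each driver is scaled to SD 1 with the same slope and drop-out rate, so the stayers' mean on it shifts by the same amount d. From the first row, d = 0.14 / sqrt(1 - 0.36) = 0.14 / 0.8 = 0.175. Then:

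- *Unpredicted part.* The Time 3 slope on Time 2 given Time 1 is r / (1 + r) = 0.6 / 1.6 = 0.375. Time 3 bias = 0.375 x 0.14 = 0.05.
- *Change.* Its SD is sqrt(2 - 2r) = 0.894. Time 2 bias = 0.894 x 0.175 = 0.16. The Time 3 change has slope (1 - r) / (2 - 2r) = 0.5 on it, so Time 3 bias = 0.08.
- *Level.* Time 2 bias = (1 - r) x 0.175 = 0.07. Time 1 and Time 3 shift equally, so Time 3 bias = (0.6 - 0.6) x 0.175 = 0.

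**Step 4: against sampling error.** With 20% lost, 40 to 80 stayers remain per arm. The SE of the change contrast is sqrt(2 x (2 - 2r) / n) = sqrt(1.6 / 40) = 0.20 to sqrt(1.6 / 80) = 0.14. A Time 3 bias of 0.05 is 0.25 to 0.36 of one SE. A Time 2 bias of 0.14 is 0.7 to 1.0 of one SE.

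**Step 5: other inputs.** The settings were total N of 100 or 200, correlation 0.3 to 0.7 between successive surveys, 15% or 30% drop-out, and an odds ratio of 2 per SD, with the same mechanism in both arms for the detection rates.

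- Unpredicted part: Time 1 test 4-6%; Time 2 test 36-79% (N = 100) and 63-98% (N = 200).
- Time 2 level: Time 1 test 10-54% and 16-86%; Time 2 test 65-87% and 93-100%.
- Complete-case Time 3 contrast, true value -0.40 (lower is better here), drop-out driven by the unpredicted part: -0.43 to -0.50 if that mechanism acts in the intervention arm only; about -0.40 if it acts in both arms.

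**Step 6: keeping Time 2.** Under the step 2 mechanisms, an analysis that kept every observed Time 2 score removed the Time 3 bias.

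**The case against.** The best defence is that a baseline attrition comparison is an ordinary descriptive step, that the SAP says only that differences were examined, and that the larger gap is the unstated handling of missing surveys in the primary model. A model that keeps all Time 2 scores would make the diagnostic largely unnecessary, and the diagnostic alone corrects nothing. This stands, and it is why the fix reaches the primary analysis.

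Four stronger readings are tempting, and the documents do not support them.

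- *The check is blind to any drop-out related to Time 2.* This is exact only for the part that Time 1 does not predict. Drop-out on Time 2 level is flagged in 18-32% of trials with arms pooled, and more often if both arms behave this way.
- *Splitting the Time 1 comparison by arm would be useless.* This too holds only for the unpredicted part. Otherwise detection rises, to about 30-54% for level and 20-35% for change.
- *The reported contrasts are biased.* That needs drop-out that differs by arm, and a model that discards incomplete cases. The documents establish neither. They also give no drop-out numbers, and the gift certificate depends on completing all three surveys, which encourages staying.
- *The plan treats a null comparison as proof that attrition is harmless.* It makes no such statement. The point is that the comparison could not bear that use.

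A remedy that switched the Time 3 analysis whenever Time 2 significantly predicted drop-out would also be unsound, because it makes the model depend on the data outcome by outcome.

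**Conclusion.** The point holds as a limitation of the stated check. For drop-out driven by response that Time 1 does not predict, the check performs at its 5% error rate, against about 70-95% for a Time 2 comparison adjusted for Time 1. For drop-out on level or change its power is reduced, not absent.

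Under the main assumptions (correlation 0.6, 20% drop-out, Time 2-related in the intervention arm only, complete-case analysis), bias is about +0.07 to +0.15 SD at Time 2 and 0 to +0.08 SD at Time 3. With the second set of inputs the Time 3 contrast was overstated by 0.03 to 0.10 SD. With a shared mechanism the bias is about zero. The sign assumes that those doing worse leave.

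I also assume that completing the protocol means completing the surveys. This is a cheap and worthwhile improvement; nothing here shows that the trial's results are wrong.

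**What to change.** **Preliminary Data Analyses**

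- Split non-completers into those with no Time 2 survey and those with Time 2 but no Time 3, and give the counts by arm.
- For the second group, report within each arm the difference in Time 2 score, adjusted for Time 1, between caregivers without and with Time 3. Give it as an estimate with a confidence interval, not as a pass/fail test.
- State that the Time 1 comparison alone will not be cited as evidence that attrition is ignorable.

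**Primary Analyses**

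- State how the existing model treats a missing survey.
- For every outcome, whatever the diagnostic shows, report a likelihood-based repeated measures model, or multiple imputation, that keeps all observed Time 2 scores.

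**Cost.** A few lines of text and analyses of data already collected, which can be done retrospectively. The hypotheses list 11 main and 6 exploratory items, so there are up to 17 x 2 = 34 extra regressions. If each were read at the 5% level, about 34 x 0.05 = 1.7 chance signals would be expected, which is a further reason to report estimates. The diagnostic says nothing about caregivers lost before Time 2.

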### **Primary Analyses:**

To examine intervention efficacy, outcomes were assessed across time that included both short-term and long-term impacts. Separate 2 (condition: intervention, waitlist control) x 3 (time: Time 1, Time 2, Time 3) repeated measures general linear models were used to examine mean group differences across time between the intervention and waitlist control groups for each outcome measure. The repeated measures analyses indicated whether there was any significant change across time for each outcome measure based on whether participants received the intervention or had not received the intervention. Employment status was included as a covariate in all analyses to control for the significant difference found at baseline between the two conditions. For significant outcomes that did not meet the Sphericity assumption, the Greenhouse-Geisser correction was used and reported for degrees of freedom. For outcome measures that were found to be significant, additional post-hoc pairwise comparison with a Bonferroni correction were conducted to examine where the change occurred across the different data collection periods (i.e., Time 2, Time 3).

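### The named 2 x 3 repeated-measures GLM by default uses only caregivers with all three surveys, and no analysis population or missing-data method is stated; any resulting bias is conditional and of unknown size and direction

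*Combined protocol and SAP*

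**What the plan says.** Under Primary Analyses, the SAP states: "Separate 2 (condition: intervention, waitlist control) x 3 (time: Time 1, Time 2, Time 3) repeated measures general linear models were used". It adds: "For significant outcomes that did not meet the Sphericity assumption, the Greenhouse-Geisser correction was used and reported for degrees of freedom". Employment status is the only covariate.

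Under Preliminary Data Analyses, it says: "Data were cleaned including examining missing data and addressing any out-of-range values". What was then done about missing values is not said. The same section describes an attrition check that compares select characteristics and "the Time 1 scale scores for each outcome between participants who completed the study protocol and those who did not". The check is not described by arm, and no consequence for the primary analysis is given.

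The protocol, under Design and Procedures, places randomisation after the Time 1 survey and says: "In total, participants completed 3 surveys". Time 3 falls 45 days after Time 2. Neither the protocol nor the SAP gives a sample size, a retention figure, a number analysed, an analysis population or a missing-data method.

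**The concern.** A repeated-measures GLM with a sphericity test and Greenhouse-Geisser degrees of freedom is normally fitted with one row per person and all time points present. By default a caregiver missing Time 2 or Time 3 leaves the model, together with the surveys that were answered. Because randomisation follows Time 1, such a caregiver is a randomised participant with a usable baseline and perhaps a usable Time 2.

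The SAP itself separates completers from others, so non-completion happened or was expected. One arm had a 6-week coaching program and the other waited, so different loss by arm is plausible, though not shown. If loss differs by arm and is related to the outcome, the comparison among completers is no longer the randomised one. Even unrelated loss costs precision.

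The attrition check does not settle this. It looks at baseline variables, is not described by arm, and corrects nothing. It cannot detect loss that depends on scores after Time 1.

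**Working it through.** The plan has no figure to reproduce. Everything below is an illustration on **assumed** inputs: true effect 0, SD 1, correlation 0.6 between all surveys, no covariate, higher score = worse (so a negative bias favours the intervention). Control loss is 10% at random. Intervention loss is logistic in one score, with 25% loss at the mean score and slope 1 per SD.

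**Step 1. Selection.** Integrating over a standard normal score, 71.4% of the intervention arm is retained. The mean of the driving score among those retained is m = -0.242. Reversing the slope gives m = +0.242. The control arm has m = 0.

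**Step 2. Completers bias.** If loss depends on the score at survey k, the bias in change from Time 1 to survey j is m × (r_jk − r_1k), with r_kk = 1.

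- *Loss of Time 3 depends on the observed Time 2 score.* At Time 2: −0.242 × (1 − 0.6) = −0.097. At Time 3: −0.242 × (0.6 − 0.6) = 0.
- *The same with unequal correlations.* With r12 = 0.5 and r23 = 0.7: Time 2 −0.121, Time 3 −0.048. With r12 = 0.7 and r23 = 0.5: Time 2 −0.073, Time 3 +0.048.
- *Slope reversed:* Time 2 +0.097.
- *Loss depends on Time 1:* −0.242 × (0.6 − 1) = +0.097 at both follow-ups.
- *Milder loss* (base 20%, slope 0.7, 78% against 90% retained): m = −0.143, so Time 2 is −0.143 × 0.4 = −0.057.
- *Same rate and mechanism in both arms* (76% retained in each): m cancels and the bias is 0.

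In the cases where loss depends on an observed score, a mixed model using all surveys has bias of about 0. Simulated Greenhouse-Geisser rejection of the condition-by-time test at nominal 5%, in the first case, is about 7% for N = 100 and 9 to 10% for N = 200. With the same mechanism in both arms it is about 5%.

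**Step 3. Loss that depends on an unseen score.** The mixed model now carries over the part of m that the observed surveys do not explain. With the slope held at its true value this is m × (1 − R²); fitting by arm among completers makes it slightly larger.

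| Loss pattern | Survey | Completers | Mixed model |
|---|---|---|---|
| Time 3 lost, depends on Time 3 | Time 3 | −0.242 × 0.4 = −0.10 | R² = 0.45: −0.242 × 0.55 = −0.13; by arm −0.14 |
| Times 2 and 3 both lost, depends on Time 2 | Time 2 | −0.242 × 0.4 = −0.10 | R² = 0.36: −0.242 × 0.64 = −0.15; by arm −0.16 |

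**Step 4. Precision under random loss d in both arms.** The variance of a change score is 2 × (1 − 0.6) = 0.8. The SE ratios below are completers to mixed model.

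- *Time 2 answered, Time 3 lost.* At Time 2, 1/√(1 − d) = 1.054 (d = 10%) and 1.118 (d = 20%). At Time 3, √{[0.8/(1 − d)] / [0.55/(1 − d) + 0.25]} = 1.016 and 1.033.
- *Both follow-ups lost.* At Time 2, √{[0.8/(1 − d)] / [0.64/(1 − d) + 0.16]} = 1.010 and 1.021.

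The precision gain at Time 2 therefore depends heavily on whether lost caregivers had answered Time 2.

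**The case against.** No passage says that incomplete caregivers were excluded. Missing data were examined during cleaning, and imputation before the GLM would fit the text. The protocol speaks of three completed surveys and pays $120.00 only once all three are done, which encourages retention. This stands in part: deletion is an inference from the model named, and the documents show an omission in reporting rather than a biased result. It does not close the point, because the schedule sentence gives no count and the SAP refers to non-completers.

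The mixed model is also not a cure. Its clear advantage needs loss that depends on scores already observed; with loss during the program it may recover little precision and can be more biased. That stands, and it limits the remedy.

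A reader might infer that caregivers were analysed by treatment received, from "based on whether participants received the intervention or had not received the intervention". The text does not support this: the sentence before it defines the factor as condition, which the protocol uses for random assignment. Loose wording is the natural reading, and a stated analysis set would remove the doubt.

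A reader might also infer that attrition inflated the benefit. With no retention reported, neither the presence nor the direction of bias can be claimed.

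**Conclusion.** The concern holds as a should-fix. The confident part is the omission: a model that by default needs all three surveys, with no analysis population, missing-data method or retention reported, and an attrition check that cannot correct for loss.

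The consequence is conditional. It is small or nil if retention was near complete, or if rate and mechanism were the same in both arms. Under the assumed 71% against 90% retention with correlation 0.6, completers bias is about 0.10 SD in either direction for loss on an observed score. Loss on an unseen score biases both methods, by 0.10 SD for completers against 0.14 or 0.16 SD for the mixed model. Under random loss of 10% or 20%, the completers SE at Time 2 is about 5 to 6% or 11 to 12% larger if Time 2 was answered, but only about 1% or 2% larger if both follow-ups were lost. None of these is an estimate for this trial.

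**What to change.** 1. Report the number analysed for each outcome and retention by arm at Time 2 and Time 3. State the analysis population and what was done with missing surveys. This comes first and may make the rest unnecessary.
2. Unless retention was essentially complete, re-analyse all randomised caregivers in their assigned condition, using every available survey. Use a likelihood-based mixed model for repeated measures with condition, time, condition-by-time, an unstructured covariance and employment status. Label it post hoc and show it beside the completers GLM.
3. If loss is material or differs by arm, add a delta-adjusted missing-not-at-random sensitivity analysis by arm, in both directions.

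Cost: step 1 is reporting only. Step 2 re-runs about 17 models on data already held (11 hypothesised plus 6 exploratory entries in the protocol's hypotheses section), with no new participants or surveys. Because the analyses are described as already done, the change comes after results are known and must be declared. Estimates may move either way, and the mixed model does not protect against loss that depends on unseen scores.

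### The pre-randomisation Time 1 score is analysed as an outcome level instead of a covariate, and no intervention-minus-waitlist difference with a confidence interval is specified at Time 2 or Time 3

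*Combined protocol and SAP*

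**What the plan says.** Under Design and Procedures, "caregivers completed the baseline/Time 1 survey and were then randomly assigned to the intervention condition or the waitlist control condition". The survey points are "Time 1 (Baseline); Time 2 (after program completion); and Time 3 (45 days after Time 2".

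Under Primary Analyses, "Separate 2 (condition: intervention, waitlist control) x 3 (time: Time 1, Time 2, Time 3) repeated measures general linear models were used", one model per outcome. The same section adds: "Employment status was included as a covariate in all analyses to control for the significant difference found at baseline between the two conditions". No other covariate is named. Outside this model, Time 1 scores appear under Preliminary Data Analyses only for the reliability check and for the attrition comparison, which uses the "Time 1 scale scores for each outcome".

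Follow-up testing is conditional: it is reserved for outcomes whose overall test reached significance. In those cases, "additional post-hoc pairwise comparison with a Bonferroni correction were conducted to examine where the change occurred across the different data collection periods", with Time 2 and Time 3 given as the periods meant. No adjusted difference, effect size or confidence interval is mentioned anywhere.

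**The concern.** There are two linked problems.

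1. **Missing estimates.** The hypotheses are between-arm: the trial "hypothesized significant improvements for participants in the intervention condition as compared to participants in the waitlist control condition", and it sets out to assess short-term and long-term impact. The quantities that answer this are the arm difference at Time 2 and the arm difference at Time 3, each with its uncertainty. The plan promises only a significance statement about change across time, then a pairwise step whose direction (between arms or between time points) is not stated. For an outcome that misses significance, no estimate is planned at all, so a reader cannot tell a null effect from an imprecise one.

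2. **Lost precision.** Time 1 cannot be affected by treatment. Making it a level of the outcome means the interaction compares unadjusted changes. Using it as a covariate removes the variation in follow-up scores that it predicts. The plan adjusts for a demographic variable because it differed at baseline, but not for the baseline value of the outcome itself, which is already collected.

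Bias is not at stake. The condition-by-time test is a valid between-arm test.

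**Working it through.** **Inputs.** From the documents: three time points, Time 1 before randomisation, employment status as covariate. The documents give no N, SD, effect size, correlation or alpha, so there is no planned figure to reproduce, and every number below rests on assumptions: n per arm, SD 1, two-sided alpha 0.05, equal correlation rho between all pairs of times (compound symmetry), and employment using 1 df in both models. The SAP does not name the deciding term; condition-by-time is taken as the planned test. Effects at Time 2 and Time 3 are written d = (d2, d3), with 0 at Time 1.

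**Planned condition-by-time test.** Noncentral F with lambda = (n/2) × Σ(d_t − mean d)² / (1 − rho), df 2 and 2(2n − 3).

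**Baseline-adjusted joint test that both arm differences are zero.** Noncentral F with lambda = (n/2) × d′C⁻¹d, df 2 and 2n − 5. C is the covariance of Time 2 and Time 3 given Time 1: diagonal 1 − rho², off-diagonal rho − rho².

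**Worked case: n = 50, d = (0.4, 0.4), rho = 0.5.**
- Planned: the mean of (0, 0.4, 0.4) is 0.267 and the sum of squared deviations is 0.1067. Lambda = 25 × 0.1067 / 0.5 = 5.33, df 2 and 194, power 52%.
- Adjusted: C has 0.75 on the diagonal and 0.25 off it, so d′C⁻¹d = 2 × 0.16 / (0.75 + 0.25) = 0.32. Lambda = 25 × 0.32 = 8.0, df 2 and 95, power 70%.

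**Power, planned v adjusted:**

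| n per arm, effect (SD) | rho 0.5 | rho 0.6 | rho 0.7 | rho 0.8 |
|---|---|---|---|---|
| 50, (0.4, 0.4) | 52 v 70% | 63 v 76% | 76 v 84% | 91 v 94% |
| 50, (0.2, 0.5) | 60 v 72% | 71 v 79% | 83 v 88% | 95 v 97% |
| 50, (0.4, 0) | 52 v 57% | 63 v 66% | 76 v 78% | 91 v 92% |
| 25, (0.4, 0.4) | 28 v 39% | 34 v 44% | 44 v 52% | 62 v 67% |
| 100, (0.4, 0.4) | 84 v 95% | 91 v 97% | 97 v 99% | 100 v 100% |

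For 80% power at d = (0.4, 0.4), n per arm is 92/74/55/37 planned and 62/55/45/33 adjusted across the four correlations.

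**Simulation check** (5000 replicates, n = 50, d = (0.4, 0.4), Greenhouse-Geisser applied to the planned test): 51.7/61.8/74.8/91.3% v 69.2/74.8/83.9/94.2%. With no effect, type I error was 4.8–5.3% planned and 4.7–5.1% adjusted, so both tests are valid.

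**Precision at one follow-up.** The variance factor is 2(1 − rho) for change from Time 1 and 1 − rho² with Time 1 as covariate. Their ratio is (1 + rho)/2 = 0.75/0.80/0.85/0.90. With 50 per arm the 95% CI half-width falls from 0.40/0.36/0.31/0.25 SD to 0.34/0.32/0.28/0.24 SD.

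**The case against.** The strongest reply is that a 2 x 3 repeated measures model is a standard, valid test of differential change, so the choice of adjustment is a preference between two sound analyses, and its cost here rests wholly on assumed inputs. Both statements are true. They limit the efficiency half of the point; they do not supply the missing estimates, which depend on no assumed figure.

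Further points in the plan's favour:

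- **The adjusted test is not always better.** It has fewer denominator df. At 12 per arm, d = (0.4, 0), rho 0.8, power is 32.0% planned v 30.6% adjusted. At 20 per arm, d = (0.4, −0.2), rho 0.5, it is 37.7% v 36.8%. These deficits are small and arise in very small samples with one-time or opposite-sign effects, but N is unknown.
- **The size of the gain depends on the correlation pattern.** Under AR(1) correlation with 50 per arm (simulated, 4000 replicates), an effect of d = (0.2, 0.5) at rho 0.8 gave 82% v 83%, while an effect at Time 2 only gave 44% v 60% at rho 0.5 and 88% v 97% at rho 0.8. The direction stands; the compound-symmetry figures are not general.
- **The follow-up step names only Time 2 and Time 3**, which leans towards comparing arms at those times. The text still does not say so, and the step remains conditional on significance.

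The deciding term is also unstated. If it were the condition main effect, Time 1 would dilute an equal follow-up effect to two thirds. At 50 per arm, 0.4 SD at both times and rho 0.5, a calculation without the employment covariate gives 37% power for that term.

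**Conclusion.** The concern holds on both parts. The plan specifies no intervention-minus-waitlist difference with an interval at either follow-up, and none at all for non-significant outcomes; this follows from the text alone. It also leaves unused, as a covariate, a baseline score the trial already holds.

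Under the compound-symmetry assumptions above with 50 per arm and equal effects at both times, the power given up runs from about 18 points at rho 0.5 to about 3 at rho 0.8. In the tabulated cases it is 5 points or less when rho is 0.8 or the effect is at one time only. The actual loss cannot be computed from the documents. The planned test's validity is not in question, so this is a change that should be made, not a fatal flaw.

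**What to change.** - Model Time 2 and Time 3 as the outcomes, with condition, time, condition-by-time, the Time 1 score of the same measure, Time 1-by-time, and employment status as planned. The equivalent longitudinal model with arm means constrained equal at Time 1 would also serve.
- Use as omnibus test the joint 2-df test that both arm differences are zero (condition and condition-by-time terms together). In a model without Time 1 as outcome, the interaction alone would miss an effect that is equal at both times.
- For every outcome, significant or not, report the adjusted intervention-minus-waitlist difference with 95% CI at Time 2 and at Time 3.
- State that the Bonferroni follow-up consists of the two between-arm comparisons, with neither placed first. Say also that the 95% CIs are unadjusted estimates and that the Bonferroni result governs significance claims, since the two can disagree. This does not address multiplicity across outcomes.
- Report within-arm change descriptively only.

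The cost is SAP wording and a re-run on existing data, with no new data collection. Because the SAP describes the analyses as already done, this must be presented as a labelled post-hoc re-analysis beside the original results.
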